8.5.3 Safety Assessments

Planned time points for all safety assessments are listed in the Schedule of Activities (Section 1). All urgent safety concerns must be discussed with the sponsor immediately upon occurrence or awareness to determine if the participant should continue or discontinue treatment.

Safety will be assessed using incidence of all AEs; the incidence of SAEs; the incidence of AEs leading to withdrawal of study medication; the incidence of AEs of special interest, immunogenicity, laboratory data, ECG monitoring, physical examinations, and monitoring of BMD via DXA.

8.5.3.1 Adverse Events

The definitions of an AE or SAE can be found in [Appendix 9](#).

AEs will be reported by the participant (or, when appropriate, by a caregiver, surrogate, or the participant's legally authorized representative).

The investigator and any designees are responsible for detecting, documenting, and reporting events that meet the definition of an AE or SAE and remain responsible for following up AEs that are serious, considered related to the study medication or the study, or that caused the participant to discontinue before completing the study.

For weight change (increase or decrease) to be considered an AE, the change should be 10% or more from Baseline that cannot be explained by lifestyle modifications alone.

Contacts for SAE reporting are specified in Appendix 9.

Time Period and Frequency for Collecting AE and SAE Information

Sections 5.6.1 and 5.6.2 in the IB represent the Reference Safety Information to determine expectedness of SAEs for expedited reporting.

The collection of nonserious AEs should begin at initiation of study medication and continue until the Week 52/PTFU Visit (Section 1)..

Following the participant's written consent to participate in the study, all SAEs, whether related or not related to study medication, must be collected, including those considered by the investigator to be related to study medication or protocol-specified procedures. All SAEs will be collected through the Week 52/PTFU Visit and will be reported as described in Appendix 9.

The investigator must report any SAE occurring after the Week 52/PTFU Visit that is believed to be related to study medication or a protocol-specified procedure.

- Medical occurrences that begin before the start of study medication but after obtaining informed consent will be recorded on the appropriate Section of the eCRF

- All SAEs will be recorded and reported to sponsor or designee within 24 hours, as indicated in [Appendix 9](#)
- The investigator will submit any updated SAE data to the sponsor or designee within 24 hours of this information being available

Investigators are not obligated to actively seek AEs or SAEs in former study participants. However, if the investigator learns of any SAE, including a death, at any time after a participant has been discharged from the study, and he/she considers the event reasonably related to the study medication or study participation, the investigator must promptly notify the sponsor.

The method of evaluating intensity and assessing causality of AEs and SAEs and the procedures for completing and reporting/transmitting SAE reports are provided in [Appendix 9](#).

Method of Detecting AEs and SAEs

AEs can be spontaneously reported or elicited during open-ended questioning, examination, or evaluation of a participant. Care should be taken not to introduce bias when collecting AEs and/or SAEs. Inquiry about specific AEs should be guided by clinical judgment in the context of known AEs, when appropriate for the program or protocol.

Follow-Up and Recording of AEs and SAEs

- Nonserious AEs should be followed to resolution or stabilization, or reported as SAEs if they become serious (see [Appendix 9](#))
- Follow-up is also required for nonserious AEs that cause interruption or discontinuation of study medication and for those present at the end of study medication, as appropriate
- All nonserious AEs and SAEs must be recorded and described on the corresponding pages of the eCRF. Completion of supplemental eCRFs may be requested for AEs/SAEs and/or laboratory abnormalities that are reported/identified during the course of the study

After the initial AE/SAE report, the investigator is required to proactively follow each participant at subsequent visits/contacts. All SAEs and nonserious AEs of special interest (as defined in [Section 8.5.3.7](#)) will be followed until resolution, until the condition stabilizes, until the event is otherwise explained, or until the participant is lost to follow-up (as defined in [Section 8.3.9.3](#)).

Further information on follow-up procedures is given in [Appendix 9](#).

Regulatory Reporting Requirements for SAEs

- Prompt notification by the investigator to the sponsor of SAEs is essential so that legal obligations and ethical responsibilities towards the safety of participants and the safety of a product under clinical investigation are met

- An investigator who receives an investigator safety report describing SAEs or other specific safety information (e.g., summary or listing of SAEs) from the sponsor will file it along with the IB and will notify the IRB/IEC, if appropriate according to local requirements

Sponsor or designee will be reporting AEs to regulatory authorities and IRB/ECs according to local applicable laws including European Directive 2001/20/EC and FDA Code of Federal Regulations 21 CFR Parts 312 and 320. A suspected unexpected serious adverse reaction is a subset of SAEs and will be reported to the appropriate regulatory authorities and investigators following local and global guidelines and requirements.

Pregnancy

Urine or serum samples will be collected at each visit through the Week 52/PTFU Visit for pregnancy testing for WOCBPs. A negative serum pregnancy test is required during Screening. After the Screening Period, urine pregnancy testing will be conducted instead of serum testing at any site where it is allowed by the IRB/EC overseeing study conduct at that site.

Investigators shall counsel WOCBPs on the importance of pregnancy prevention and the implications of an unexpected pregnancy. Investigators shall advise on the use of highly effective methods of contraception (i.e., those that have a failure rate of < 1% when used consistently and correctly as discussed in [Appendix 2](#)).

If, following initiation of the study medication, it is subsequently discovered that a participant is pregnant or may have been pregnant at the time of study exposure, including during at least 5 half-lives after product administration (5 days) plus 30 days (duration of ovulatory cycle) for a total of 35 days after the end of the Double-Blind Treatment Period, the investigator must immediately notify the sponsor medical monitor/designee of this event and complete and forward a Pregnancy Surveillance Form to the sponsor designee within 24 hours of awareness of the event and in accordance with SAE reporting procedures described in [Appendix 9](#).

The study medication will be permanently discontinued in an appropriate manner (e.g., dose tapering if necessary for participant safety). Please call the sponsor medical monitor within 24 hours of awareness of the pregnancy.

Follow-up information regarding the course of the pregnancy, including perinatal and neonatal outcome and, where applicable, offspring information must be reported on the Pregnancy Surveillance Form ([Appendix 2](#)).

Any pregnancy that occurs in a female partner of a male study participant should be reported to sponsor or designee during at least 5 half-lives after product administration (5 days) plus 30 days (duration of ovulatory cycle) for a total of 35 days after the end of the Double-Blind Treatment Period. In order for the sponsor or designee to collect any pregnancy surveillance information from the female partner, the female partner must sign an ICF for disclosure of

this information. Information on this pregnancy will be collected on the Pregnancy Surveillance Form.

Laboratory Test Result Abnormalities

The following laboratory test result abnormalities should be captured on the nonserious AE eCRF page or SAE eCRF page, as appropriate. Paper forms are to be used only in the event that the electronic system is not functioning.

- Any laboratory test result that is clinically significant or meets the definition of an SAE
- Any laboratory test result abnormality that required the participant to have study medication discontinued or interrupted
- Any laboratory test result abnormality that required the participant to receive specific corrective therapy

It is expected that wherever possible, the clinical rather than laboratory term would be used by the reporting investigator (e.g., anemia versus low hemoglobin value).

Potential Drug-Induced Liver Injury

Wherever possible, timely confirmation of initial liver-related laboratory abnormalities should occur prior to the reporting of a potential DILI event. All occurrences of potential DILIs, meeting the defined criteria, must be reported as SAEs (see [Appendix 9](#) for reporting details). **Repeat laboratory testing may be performed locally**, and the results should be promptly communicated to the investigator site.

For the purpose of evaluating a potential DILI, the Baseline value is defined as the mean of the test results from analysis of samples collected during Screening and on Day 1.

Note that the evaluation processes below do not replace SAE reporting per defined criteria in [Appendix 9](#).

Evaluation of Participants with New Elevations of Aminotransferases and/or Total Bilirubin
Repeat laboratory testing (including ALT, AST, fractionated bilirubin and alkaline phosphatase) and physical examination should be performed within 48-72 hours when:

- Participants with normal Baseline aminotransferase (ALT and/or AST) values develop elevations greater than $3\times$ the ULN based upon the central lab, or
- Participants with elevated Baseline aminotransferase values experience additional increases greater than $2\times$ the Baseline (with concomitant elevations of total bilirubin $> 2\times$ ULN) AND ALT and/or AST is > 200 U/L.

If the new elevations in aminotransferases persist and the participant is symptomatic, then the drug should be discontinued, and the participant should be evaluated for other causes of liver injury or disease. The medical monitor should be contacted within 48-72 hours.

If the participant is asymptomatic, the participant should be placed under “close observation”, defined as physical examination and laboratory evaluation 2-3 times per week.

If close observation is not possible, study medication should be discontinued. The frequency of retesting can decrease to once a week or less if abnormalities stabilize or the study medication has been discontinued and the participant is asymptomatic.

Discontinuation or Temporary Interruption of Study Medication

In addition to the reasons for discontinuation described above, study medication should be discontinued or temporarily interrupted if either of the 2 following scenarios occur:

- 1) Aminotransferases (ALT and/or AST) $> 2 \times$ Baseline and aminotransferases $> 3 \times$ ULN and either:
 - i. the increase is accompanied by a concomitant increase in total bilirubin to $> 2 \times$ Baseline OR the INR concomitantly increases by > 0.2 ;

OR

 - ii. there are concomitant signs and symptoms of new-onset fatigue, nausea, vomiting, right upper quadrant pain or tenderness, fever, rash, and/or eosinophilia ($> 5\%$).
- 2) Total bilirubin increases to $> 2 \times$ ULN AND:
 - i. there are concomitant signs and symptoms of new-onset fatigue, nausea, vomiting, right upper quadrant pain or tenderness, fever, rash, and/or eosinophilia ($> 5\%$)

If the above rule is met, a potential DILI work up for competing etiologies (e.g., alcohol use, viral hepatitis, biliary obstruction, autoimmune liver disease) must be performed, and a complete liver profile including INR must be repeated within 48-72 hours. **The medical monitor should be contacted within 48-72 hours.** Study medication can be restarted only if an alternative etiology is definitively identified and liver tests (aminotransferases, total bilirubin and/or INR) have returned to Baseline.

Other Safety Considerations

Any significant worsening noted during interim or final physical exams, ECGs, or any other potential safety assessments required or not required by protocol should also be recorded as a nonserious AE or a serious AE, as appropriate, and reported accordingly. ECGs will be read and interpreted at the site or by a local reader.

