- b) ALT value $> 5 \times$ the upper limit of normal (ULN) as defined by the central laboratory
- c) AST value $> 5 \times$ ULN as defined by the central laboratory
- d) Total bilirubin > 1.5 mg/dL
- e) Serum albumin < 3.5 g/ dL
- f) Platelet count $< 100 \times 10^3/\mu\text{L}$
- g) International normalized ratio (INR) > 1.4 , unless due to therapeutic anticoagulation

[figure not shown]
- h) Fasting plasma glucose < 60 mg/dL (< 3.33 mmol/L) or > 350 mg/dL (> 19.43 mmol/L)
- i) Hemoglobin A1c ≥ 10%
- j) Fasting TGs > 500 mg/dL
- k) Estimated glomerular filtration rate (eGFR) < 30 mL/min/1.73 m² according to the Modification of Diet in Renal Disease equation
- l) Evidence of significant worsening of ALT, AST or bilirubin during the Screening Period, in the opinion of the investigator or medical monitor
- m) A centrally read DXA BMD T-Score of -2.5 or less at the femoral neck, total hip, or lumbar spine during Screening (exclusionary only if participant is 40 years of age or older)

[figure not shown]
6. Allergies and adverse drug reactions

- a) History of allergy to FGF21, PEG, or related compounds
- b) History of drug-induced liver injury (DILI)

7. Other exclusion criteria

- a) Prisoners or participants who are involuntarily incarcerated. **Note:** Under certain specific circumstances, a person who has been imprisoned may be included or permitted to continue as a participant. Strict conditions apply, and sponsor approval is required
- b) Participants who are compulsorily detained for treatment of either a psychiatric or physical (e.g., infectious disease) illness
- c) Any factor that, in the opinion of the investigator, would jeopardize the evaluation or safety of the participant or be associated with poor adherence to the protocol
- d) Participants who are incapable of completing study-related assessments (i.e., participant questionnaires) as they MUST be completed by the participant

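### When ALT and AST are both raised at baseline, the 48-72 hour liver retest needs three conditions at once, so several asymptomatic liver-test rises have no timed retest

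*Protocol*

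**What the plan says.** Protocol 8.5.3.1, under "Evaluation of Participants with New Elevations of Aminotransferases and/or Total Bilirubin", asks for repeat liver tests and a physical examination within 48-72 hours in two situations:

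- "Participants with normal Baseline aminotransferase (ALT and/or AST) values develop elevations greater than" 3 × ULN. No bilirubin condition is attached.
- "Participants with elevated Baseline aminotransferase values experience additional increases greater than" 2 × Baseline, with total bilirubin above 2 × ULN at the same time, and with ALT and/or AST above 200 U/L.

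For these rules "the Baseline value is defined as the mean of the test results from analysis of samples collected during Screening and on Day 1". If the aminotransferase rise persists, a symptomatic participant stops drug. An asymptomatic one goes under close observation 2-3 times per week, and "If close observation is not possible, study medication should be discontinued".

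The same section has a stop-or-interrupt rule. Scenario 1 is ALT and/or AST above both 2 × Baseline and 3 × ULN, plus one of: bilirubin above 2 × Baseline, an INR rise above 0.2, or listed symptoms or eosinophilia above 5%. Scenario 2 is bilirubin above 2 × ULN with those symptoms or signs. If either is met, "a complete liver profile including INR must be repeated within 48-72 hours".

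For potential drug-induced liver injury, "Wherever possible, timely confirmation of initial liver-related laboratory abnormalities should occur prior to the reporting of a potential DILI event". No number of hours or days is attached to that step. Appendix 9 defines such a case as ALT or AST above 3 × ULN with bilirubin above 2 × ULN, no initial cholestasis and no other apparent cause, and requires SAE reporting.

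Protocol 8.3.2 excludes ALT and AST only above 5 × "the upper limit of normal (ULN) as defined by the central laboratory", and bilirubin only above 1.5 mg/dL. Raised baselines are therefore eligible.

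**The concern.** The heading announces aminotransferases and/or bilirubin. Yet bilirubin alone triggers nothing, and for a raised baseline the aminotransferases alone trigger nothing either. The early-warning step also asks for two things that stop scenario 1 does not: bilirubin above 2 × ULN, and ALT or AST above 200 U/L. A participant can therefore meet the stop rule without ever having met the retest rule.

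What is at stake is safety follow-up. An asymptomatic participant with compensated cirrhosis could have a large rise in liver tests, continue weekly dosing, and have no required repeat test before the next visit. SAP 4.3.5 itself lists ALT or AST above 3 × or 5 × ULN, and bilirubin above 2 × ULN, as separate categories of potential hepatotoxicity. The analysis would flag results that the protocol does not require anyone to recheck by a set time.

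**Working it through.** **Inputs.** The thresholds are those of Protocol 8.5.3.1 and the entry limits those of 8.3.2. The visit intervals (4 weeks through Week 24, then 8 weeks, each ± 5 days) come from 8.1. The documents give no ULN values, so I assume 35-50 U/L for ALT and AST and 1.0-1.2 mg/dL for bilirubin. Each result below holds across that range.

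**Rules.** Write A for ALT or AST, B for total bilirubin and BL for Baseline. With both enzymes raised at baseline and no listed symptoms or eosinophilia, scenario 2 and the symptom limb of scenario 1 cannot apply. Two routes to a timed retest remain:

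- Retest bullet: A > 2 × BL and B > 2 × ULN and A > 200 U/L.
- Stop scenario 1: A > 2 × BL and A > 3 × ULN and (B > 2 × BL or INR rise > 0.2).

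**Cases that meet neither** (ALT and AST in U/L, B in mg/dL)

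| Group | ALT | AST | B | INR | Retest bullet fails because | Stop scenario 1 fails because |
|---|---|---|---|---|---|---|
| 1 | 60→600 | 60→500 | 0.8→0.8 | stable | 0.8 ≤ 2 × 1.0 = 2.0 | 0.8 ≤ 2 × 0.8 = 1.6; INR stable |
| 2 | 150→300 | 120→240 | 0.8→2.5 | any | 300 = 2 × 150 and 240 = 2 × 120, so neither is above 2 × BL | same |
| 3 | 60→180 | 55→150 | 1.5→2.9 | stable | 180 ≤ 200 | 2.9 ≤ 2 × 1.5 = 3.0; INR stable |
| 4 | 60→60 | 60→60 | 0.8→2.5 | any | 60 is not > 2 × 60 | 60 ≤ 3 × 35 = 105 |

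- Group 1 is an aminotransferase rise with bilirubin at or below both 2 × ULN and 2 × BL. Here ALT reaches 600/50 = 12 to 600/35 = 17 × ULN.
- Group 2 has A above 3 × ULN and B above 2 × ULN, but A at or below 2 × BL. Here 300 > 3 × 50 = 150 and 2.5 > 2 × 1.2 = 2.4, so the potential-DILI cut-offs are met. ALT is 300/50 = 6.0 to 300/35 = 8.6 × ULN. Because 5 × ULN is eligible at entry, this group can reach 2 × 5 = 10 × ULN, or 350-500 U/L.
- Group 3 is a narrow corner. B must lie above 2 × ULN and at or below 2 × BL, so baseline bilirubin must be above ULN, while entry allows at most 1.5 mg/dL. A must exceed 2 × BL yet be at most 200, so baseline ALT must be below 100. On-treatment ALT must lie above 3 × ULN (105-150) and at or below 200 U/L.
- Group 4 is bilirubin above 2 × ULN with A at or below 3 × ULN. At these ULNs 3 × ULN is at most 150 U/L, so the 200 U/L condition cannot be met.

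**The list is not complete.** ALT 150→300, AST 120→240, B 0.8→1.9 with INR up by 0.3 meets neither rule and falls in none of the four groups: A is not above 2 × BL, and 1.9 ≤ 2.0.

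**Contrast.** From a normal baseline, ALT 35→160 triggers the retest, since 160 > 3 × 50 = 150 (3.2 to 4.6 × ULN).

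**Stop without early warning.** ALT 60→180 with B 0.8→1.9 meets stop scenario 1 (180 > 120, 180 > 150, 1.9 > 1.6). It fails the retest bullet (1.9 ≤ 2.0 and 180 ≤ 200).

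**Time to next scheduled chemistry.** Through Week 24: 28 + 5 + 5 = 38 days at most. After Week 24: 56 + 5 + 5 = 66 days at most.

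**The case against.** The best reply is that nobody would ignore a tenfold ALT rise. Investigators must document review of every laboratory safety report (8.5.4) and may repeat any test. They are to interrupt dosing when they judge a result puts the participant at risk (8.4.6.2) and to raise urgent concerns with the sponsor at once (8.5.3). Clinically significant results are recorded as adverse events, and groups 2 and 3 may require SAE reporting within 24 hours under Appendix 9. The DMC and the blinded sponsor monitor safety (6.3.3). All this stands, and a reader who inferred that these participants go unwatched would be wrong. But each safeguard depends on judgment or sets no retest deadline, and none starts close observation. Groups 1 and 4 do not meet the potential-DILI cut-offs.

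Other limits also stand:

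- A reader might infer that every raised baseline is affected. The first bullet speaks of normal ALT and/or AST, and the text does not settle whether a participant with one normal enzyme falls under it. The gap is certain only when both are raised.
- A reader might infer that those who meet the stop rule also lack a timed retest. They do not, because the stop rule orders one.
- The bilirubin condition stands in brackets and could be read as optional. Group 1 above 200 U/L would then be covered. Groups 2, 3 and 4, and group 1 at or below 200 U/L, would not.
- The protocol does not say that the retest step must precede the stop rule. That ordering is a clinical expectation.
- Earlier studies showed ALT and AST falling, Table 4 predicts ALT changes of -16.7% to -26.7%, and the risk summary lists no liver signal. This argues for low frequency. It also makes a doubling on treatment unexpected and worth confirming promptly.

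**Conclusion.** The concern holds for participants with both ALT and AST raised at baseline and no listed symptoms or eosinophilia. At least four groups of liver-test rise have no objective, time-limited retest. Groups 1, 2 and 4 are broad and group 3 is narrow. The groups are examples: the documents do not support reading them as a full list.

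The result rests on reading the three conditions of the bullet as joint. The numerical examples also rest on the assumed ULNs. How many participants would be exposed cannot be derived, because the documents report no baseline distribution. A reader might infer harm to the efficacy results, but nothing in the gap itself touches an efficacy analysis. This is a cheap improvement to safety monitoring.

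**What to change.** In Protocol 8.5.3.1:

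1. Replace the raised-baseline bullet with: ALT and/or AST above 2 × Baseline and above 3 × ULN.
2. Add total bilirubin above 2 × ULN as a separate retest trigger.
3. Extend the sentence on persisting elevations to name total bilirubin as well as aminotransferases. Otherwise a bilirubin-only retest leads to no stated next step and no close observation.

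The first two reuse the stop rule's cut-offs. Any case meeting scenario 1 meets trigger 1, and any case meeting scenario 2 or the present raised-baseline bullet meets trigger 2, so nothing now covered is lost. Clinicians may adjust the cut-offs provided the retest trigger stays no stricter than the stop rule. They may also add bilirubin above 2 × Baseline, or an INR rise above 0.2, as a trigger when aminotransferases are raised. That would catch the further example shown in the check, which the two triggers alone miss.

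The cost is a short amendment, some repeat tests and close-observation visits, and possibly a few discontinuations where close observation is not possible. Those participants would have the biopsy at early termination if they had completed Week 20 (8.5.1.1), and would count as nonresponders if the biopsy were missing (9.5.2.1). Endpoints, sample size and analysis methods do not change. Enrollment had closed by protocol version 4.0 and SAP 7.1 sets a Week 52 data cut-off of 8 October 2020, so an amendment helps only participants still on treatment when it takes effect. The wording should also be corrected before it is reused in any later protocol.
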